6.10.3. Serious Adverse Events (SAEs)

A listing of patients with SAEs (including death) will be produced.

6.10.4. Adverse Events Leading to Discontinuation

A listing of patients with AEs leading to discontinuation from study will be provided.

6.10.5. Special Safety Topics

A listing of patients with all AESIs defined in Section [6.10.5](#) will be provided.

6.10.5.1. Severe/Serious Gastrointestinal Adverse Events

A listing of patients with severe/serious gastrointestinal AEs, such as nausea, vomiting, and diarrhea will be provided.

Only the PTs in the gastrointestinal SOC MedDRA with serious/severe cases will be considered as AESIs.

6.10.5.2. Hypoglycemia

Only hypoglycemic events outside of hypoglycemic clamp procedure are applicable here. A listing of clinically significant hypoglycemia (plasma glucose <54 mg/dL) and severe hypoglycemia events will be provided. A listing of patients with hypoglycemic events will be provided. The category of hypoglycemic events (see [Table GPHG.7](#) for details) will be presented. A summary will be provided by treatment. The incidence of hypoglycemia will be reported.

Severe/Serious hypoglycemia will be considered as AESIs.

Table GPHG.7. Definitions of Hypoglycemic Event Categories

	Symptoms and/or Signs of Hypoglycemia	Plasma Glucose Level
Glucose alert value	Yes/No/Unknown	≤ 70 mg/dL (3.9 mmol/L)
Documented symptomatic hypoglycemia	Yes	
Documented asymptomatic hypoglycemia	No	
Documented unspecified hypoglycemia	Unknown	< 54 mg/dL (3.0 mmol/L)
Clinically significant hypoglycemia	Yes/No/Unknown	
Documented symptomatic hypoglycemia	Yes	
Documented asymptomatic hypoglycemia	No	
Documented unspecified hypoglycemia	Unknown	

Severe hypoglycemia: defined as an episode with severe cognitive impairment requiring the assistance of another person to actively administer carbohydrate, glucagon, or other resuscitative actions. Severe hypoglycemia will be reported as an SAE.

Nocturnal hypoglycemia: defined as any hypoglycemic event that occurs between bedtime and waking.

To avoid duplicate reporting, all consecutive plasma glucose values ≤ 70 mg/dL (3.9 mmol/L) occurring within a 1-hour period may be considered to be a single hypoglycemic event.

6.10.5.3. Severe, Persistent Hyperglycemia

Data on episodes of severe, persistent hyperglycemia will be reported by the investigator during the study. Events of interest related to hyperglycemia are those that require rescue therapy, per the criteria in Protocol Section 9.2.2.3.

A listing of rescue medication for hyperglycemia will be provided (also noted in Section [6.5](#)).

6.10.5.4. Pancreatitis

A listing of patients with pancreatitis (including investigator-reported and adjudicated) will be provided. Adjudication assessment results will be reported in the listing.

Treatment-emergent adjudication-confirmed pancreatitis will be considered as AESI.

6.10.5.5. Thyroid Malignancies and C-Cell Hyperplasia

A listing of patients with thyroid malignancies and C-cell hyperplasia (search criteria provided in [Appendix 1](#)) will be provided.

Thyroid malignancies and C-cell hyperplasia will be considered as AESI.

6.10.5.6. Major Adverse Cardiovascular Events (MACE)

A listing of patients with MACE (including investigator-reported and adjudicated) will be provided. Adjudication assessment results will be reported in the listing.

Only positively adjudicated MACE will be considered as AESI.

6.10.5.7. Arrhythmias and Cardiac Conduction Disorders

A listing of patients with arrhythmias and cardiac conduction disorders (search criteria provided in [Appendix 1](#)) will be provided.

Severe/serious treatment-emergent arrhythmias and cardiac conduction disorders will be considered as AESI. The cardiovascular events will include clinically relevant rhythm and conduction disorders.

6.10.5.8. Hypersensitivity Events

A listing of patients with hypersensitivity reactions (search criteria provided in [Appendix 1](#)) will be provided.

Only the serious/severe cases of hypersensitivity will be considered as AESIs.

6.10.5.9. Injection Site Reactions

Injection-site assessments for local tolerability will be conducted, when reported as an AE from a patient, or a clinical observation from an investigator.

A listing of patients with reported injection-site reactions (e.g., edema, erythema, induration, itching, and pain) will be provided. Detailed search criteria can be found in [Appendix 1](#).

Only the severe/serious injection site reactions (e.g., abscess, cellulitis, erythema, hematomas/hemorrhage, exfoliation/necrosis, pain, subcutaneous nodules, swelling, indurating, inflammation) will be considered as AESIs.

6.10.5.10. Diabetic Retinopathy Complications

A listing of patients with diabetic retinopathy complications (search criteria provided in [Appendix 1](#)) will be provided.

The cases with repeat fundoscopy during the course of the trial, based on clinical suspicion of worsening retinopathy that have either findings of de novo retinopathy or progression of retinopathy, and severe/serious adverse events from the PTs for diabetic retinopathy complications (search criteria provided in [Appendix 1](#)), will be classified as an AESI.

6.10.5.11. Hepatobiliary Disorders

A listing of patients with events of biliary colic, cholecystitis, or other suspected events related to gallbladder disease will be provided. Detailed search criteria are provided in [Appendix 1](#).

Severe/serious hepatobiliary disorders will be considered as AESIs.

6.10.5.11.1. Hepatic Monitoring

The patients' liver disease history and associated person liver disease history data will be listed. Concomitant medications acetaminophen/paracetamol, that have potential to cause hepatotoxicity, will be listed. Results from any hepatic monitoring procedures, such as a magnetic resonance elastography (MRE) scan, and biopsy assessments will be listed, if performed.

Hepatic risk factor assessment data will be listed. Liver related signs and symptoms data will be listed, and it will be summarized by treatment if ≥ 10 patients with such data. Alcohol and recreational drug use data will also be listed.

All hepatic chemistry, hematology, coagulation, and serology data will be listed. Values outside the reference ranges will be flagged on the individual patient data listings.

6.10.5.12. Acute Renal Events

A listing of patients with acute renal events (search criteria provided in [Appendix 1](#)) will be provided.

Severe/serious acute renal events will be considered as AESI.

6.10.5.13. Metabolic Acidosis, Including Diabetic Ketoacidosis

A listing of patients with metabolic acidosis (search criteria provided in [Appendix 1](#)) will be provided.

Severe/serious Metabolic Acidosis, including Diabetic Ketoacidosis will be captured as AESIs.

6.10.5.14. Amputation/Peripheral Revascularization

A listing of patients with amputation and peripheral revascularization (search criteria provided in [Appendix 1](#)) will be provided.

Amputation/Peripheral revascularization will be considered as AESIs.

6.10.5.15. Major Depressive Disorder/Suicidal Ideation

A listing of patients with major depressive disorder/suicidal ideation (search criteria provided in [Appendix 1](#)) will be provided.

The severe/serious major depressive disorder/suicidal ideation or behavior will be captured as AESI.

6.10.6. Vital Signs

Descriptive summaries of vital signs will be provided for actual values of Day 1, Day 8, Day 15, Day 29, Day 57, Day 78 by treatment for each period, and by treatment only, and change from Day 1 values by treatment for each period, and by treatment only. Plots of mean vital signs and mean changes from Day 1 over time will be provided by treatment for each period.

The treatment-emergent abnormal vital signs will be listed. The criteria for identifying patients with treatment-emergent vital sign abnormalities are stated in [Table GPHG.8](#).

Table GPHG.8. Categorical Criteria for Treatment-Emergent Abnormal Blood Pressure and Pulse Measurements

Parameter	Low	High
Systolic BP (mmHg) (Supine or sitting – forearm at heart level)	≤90 and decrease from baseline ≥20	≥140 and increase from baseline ≥20
Diastolic BP (mmHg) (Supine or sitting – forearm at heart level)	≤50 and decrease from baseline ≥10	≥90 and increase from baseline ≥10
Pulse (bpm) (Supine or sitting)	<50 and decrease from baseline ≥15	>100 and increase from baseline ≥15

Abbreviations: BP = blood pressure; bpm = beats per minute.

For PD parameters of systolic, diastolic blood pressure, and pulse rate during hypoglycemic clamp procedures, see Section 6.9 for analyses details.

6.10.7. *Electrocardiogram*

Electrocardiograms will be performed for safety monitoring purposes only. Any clinically significant ECG findings entered as AEs will be included in AE summaries.

6.10.8. *Safety Laboratory Parameters*

All laboratory data will be reported in the International System of Units and conventional units.

Descriptive summaries of clinical chemistry, hematology, and endocrine (calcitonin) data will be provided for actual values of Day 1 predose, Day 29, Day 78, and their changes from Day 1 will by treatment for each period, and by treatment only.

Additionally, clinical chemistry, hematology, urinalysis, and endocrine (calcitonin) data outside the reference ranges will be listed.

If any safety lab measurements are (1) below the quantification limit (e.g. < QL), $\frac{1}{2} \times QL$ may be used for the calculation of summary statistics; (2) above the quantification limit (e.g. > QL), $1.1 \times QL$ may be used for the calculation of summary statistics, if deemed appropriate.

6.11. *Evaluation of Immunogenicity*

Baseline immunogenicity sample is collected on Day 1 pre-dose of period 1. The immunogenicity tables will be presented with only one overall column. The listings will report treatment and period.

For the treatment-emergent (TE) antidrug antibody (ADA)-positive patients, the distribution of maximum titers may be described.

The frequency and percentage of patients with preexisting ADA and with TE ADA-positive (TE-ADA+) to tirzepatide may be tabulated.

If cross-reactive antibodies to native GIP and GLP-1, neutralizing antibodies against tirzepatide activity on GIP and GLP-1 receptors, or neutralizing antibodies against native GLP-1 and GIP are performed, the frequency and percentage of each may be tabulated.

A listing will be provided of immunogenicity assessments. This includes the tirzepatide concentration from a simultaneous pharmacokinetic sample and the clinical interpretation result (ADA Present, ADA Not Present, ADA Inconclusive, or Missing). A listing of TEAE for patients with TE ADA+ or Injection Site Reaction or Potential Hypersensitivity may be provided.

Cases of TE-ADA+ that are associated with AEs of either severe/serious hypersensitivity or severe/serious injection site reaction will be classified as AESI.

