6.1. Populations for Analyses

For the purpose of analysis, [Table GPHG.2](#) defines 3 analysis sets.

Table GPHG.2. Analysis Populations/Data Sets

Population/Data Set	Definition
All randomized population	All patients who are randomly assigned to a treatment sequence.
Safety population	All randomized patients who are exposed to at least 1 dose of study drug (tirzepatide or placebo), regardless of whether they completed all protocol requirements.
PD analysis set *	Evaluable PD data from all randomized patients who are exposed to at least 1 dose of study drug and complete both hypoglycemic clamp procedures.

Abbreviations: PD = pharmacodynamic.

* Protocol deviations will be considered for their severity/impact and taken into consideration whether subjects should be excluded from PD analysis set for hypoglycemic clamp data related analyses.

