6.2. General Considerations

Statistical analysis of this study will be the responsibility of Eli Lilly and Company (Lilly) or its designee. Any change to the statistical methods described in the protocol will require a protocol amendment only if it changes a principal feature of the protocol. Any other change to the statistical analyses and the justification for the change will be documented in this SAP.

Unless otherwise specified, safety analyses will be conducted on safety population ([Table GPHG.2](#)) and pharmacodynamic (PD) analyses will be conducted on PD analysis set ([Table GPHG.2](#)).

Unless otherwise noted, all tests of treatment effects will be conducted at a 2-sided alpha level of 0.05, and the CI will be calculated at 95%, 2-sided.

If deemed necessary, additional analyses (e.g. linear mixed-effect models) of the endpoints on log transformed data will be conducted.

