Hypoglycemia awareness will be evaluated based on the patients' response (yes/no) to the question "Do you feel hypoglycemic?" during induced hypoglycemia. These data will be recorded in eCRF.

Hypoglycemia awareness will be assessed twice (0 and 30 minutes) at each of the 3 plateaus (target levels of PG of 100 mg/dL [5.5 mmol/L], 63 mg/dL [3.5 mmol/L,] and PG of 45 mg/dL [2.5 mmol/L]) (see [Table GPHG.5](#) for details).

- If the patient answered "yes" at least once when the question was asked twice in the same plateau, the patient is aware of hypoglycemia during induced hypoglycemia at that target PG level. If the patient answered "no" to the question when asked twice in that plateau, the patient is unaware of hypoglycemia. If there is only one non-missing value, it will be used as the measurement.

Hypoglycemia awareness will be assessed once when recovery PG of 72 mg/dL (4.0 mmol/L) is reached (see [Table GPHG.5](#) for details).

Vital signs

Vital signs (that is, systolic blood pressure, diastolic blood pressure, pulse rate, and body temperature) at target PG of 100 mg/dL (5.5 mmol/L), 63 mg/dL (3.5 mmol/L), and 45 mg/dL (2.5 mmol/L) will be measured twice at each of the 3 plateaus (see [Table GPHG.6](#) for details).

- Mean vital signs (systolic blood pressure, diastolic blood pressure, and pulse rate) at target PG of 100 mg/dL (5.5 mmol/L), 63 mg/dL (3.5 mmol/L), and 45 mg/dL (2.5 mmol/L) will be calculated as the mean of the 2 measurements taken at each of these 3 plateaus for PD analyses. If there is only one non-missing value, it will be used as the measurement.

Vital signs will be measured once when recovery PG of 72 mg/dL (4.0 mmol/L) is reached (see [Table GPHG.6](#) for details).

Table GPHG.6. Vital Signs During Hypoglycemic Clamp Procedure on Day 80

Clamp PG Level	Planned Timepoints of Collecting Vital Signs
100 mg/dL (5.5 mmol/L)	-30 minutes 0 minutes
63 mg/dL (3.5 mmol/L)	I minutes I + 30 minutes
45 mg/dL (nadir; 2.5 mmol/L)	J minutes J + 30 minutes
72 mg/dL (4.0 mmol/L)	K minutes

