The above changes in vital signs during induced hypoglycemia will be summarized by treatment, and will be analyzed respectively in a manner similar to the primary PD analysis using a linear mixed-effect model.

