The status of whether patients require glucose infusion to attain recovery and whether patients recovered spontaneously at $J+45$ minutes will be analyzed in a similar manner to the secondary analyses on hypoglycemia awareness with nonparametric McNemar test.

Counter-regulatory hormone responses, and responses of insulin and C-peptide, and vital signs during induced hypoglycemia

- Change in mean glucagon, insulin, C-peptide, growth hormone, cortisol, adrenaline, and noradrenaline concentrations from target PG nadir of 45 mg/dL (2.5 mmol/L) to 72 mg/dL (4.0 mmol/L)

The above changes in counter-regulatory responses will be analyzed in a manner similar to the primary PD analysis using a linear mixed-effect model.

- Change in vital signs (systolic blood pressure, diastolic blood pressure, and pulse rate) from target PG nadir of 45 mg/dL (2.5 mmol/L) to 72 mg/dL (4.0 mmol/L)

The above changes in vital signs during induced hypoglycemia will be analyzed in a manner similar to the primary PD analysis using a linear mixed-effect model.

Additional exploratory PD parameters (counter-regulatory responses, vital signs, and AUC_{GIR}) for analyses

The following PD parameters collected at ambient PG sample (only glucagon), three 30-min target PG plateaus (5.5 mmol/L, 3.5 mmol/L, and nadir [2.5 mmol/L]) and recovery [4.0 mmol/L] on Day 80 will be summarized by treatment using descriptive statistics. Corresponding plots of mean and standard deviations of these PD parameters over the target PG levels will be provided by treatment.

These PD parameters will be analyzed in a manner similar to the primary PD analysis using a linear mixed-effect model.

- Counter-regulatory hormone responses (glucagon, growth hormone, cortisol, adrenaline, and noradrenaline), and responses of insulin and C-peptide to induced hypoglycemia
 - Only glucagon will also be collected at ambient PG sample under pre-prandial state, prior to clamp initiation on Day 79
- Vital signs (systolic blood pressure, diastolic blood pressure, and pulse rate) during induced hypoglycemia
- AUC_{GIR} [mg/kg]
 - It will be calculated at each of the 3 plateaus (30 minutes each), and at recovery period ($J+30$ minutes to K minutes).

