6.10. Safety Analyses

Safety measures include, but not limited to, AEs, treatment-emergent adverse events (TEAEs), serious adverse events (SAEs), adverse events of special interest (AESIs), vital signs, and safety laboratory measures.

Unless specified otherwise, safety analyses will be performed on the safety population.

Unless specified otherwise, safety listings will display values/events during all study periods (i.e., treatment periods, washout, and follow-up period). Listings of AEs, death, SAE may include (but not limited to): patient identification (ID) number, age, sex, race, treatment, dose, Medical Dictionary for Regulatory Activities (MedDRA) System Organ Class (SOC), Preferred Term (PT), and time of onset from the first dose of study drug, duration of the AE, seriousness, severity, relatedness to study drug, action taken, and outcome, as appropriate. Additional safety listings will be provided for safety parameters other than AEs in related sections below. Treatment, and treatment period will be displayed in listings.

For safety measurements, summary statistics will be provided by treatment. A summary will be provided for AEs with frequency ≥ 10 patients with such event.

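### By-treatment summaries of clamp blood pressure and pulse cover only patients who complete both clamps; one descriptive safety-population table would cheaply include the rest

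*SAP*

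**What the plan says.** **Protocol.** Section 10.3.1.2 counts vital signs taken during the clamps among the safety parameters to be listed and summarised. Section 10.3 runs safety analyses in all enrolled patients, whether or not they completed. The same 10.3.1.2 refers the reader to the PD section for clamp vital signs. Section 10.3.3.2 and the synopsis then place the descriptive summary of clamp blood pressure and pulse among the PD measures, and 10.3 restricts PD analyses to patients who complete both clamps.

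**SAP, safety side.** Section 6.10 says in general: "For safety measurements, summary statistics will be provided by treatment". Section 6.10.6 is specific. Vital-sign summaries are "provided for actual values of Day 1, Day 8, Day 15, Day 29, Day 57, Day 78 by treatment for each period", which stops before the clamp on Day 80. Clamp values are sent elsewhere: "For PD parameters of systolic, diastolic blood pressure, and pulse rate during hypoglycemic clamp procedures, see Section 6.9 for analyses details".

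**SAP, PD side.** Section 6.9.2.2 covers changes from the 100 mg/dL plateau: "The above changes in vital signs during induced hypoglycemia will be summarized by treatment". Section 6.9.2.3 covers the plateau and recovery values themselves, which "on Day 80 will be summarized by treatment using descriptive statistics". Under Section 6.2, unless otherwise specified, "pharmacodynamic (PD) analyses will be conducted on PD analysis set", and nothing else is specified for clamp vital signs. Table GPHG.2 in Section 6.1 defines that set as "Evaluable PD data from all randomized patients who are exposed to at least 1 dose of study drug and complete both hypoglycemic clamp procedures".

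**The concern.** A patient can finish the Period 1 clamp, have all its readings recorded, and then leave. Those readings enter no by-treatment vital-sign summary, because the patient has no second clamp. Inclusion therefore depends on something that happens after the readings were taken.

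Leaving may be related to the readings. Protocol 8.1.1 allows permanent discontinuation for an adverse event diagnosed during the clamp, and a patient who stops study drug also leaves the study. Protocol 3.2 reports a dose-dependent rise in heart rate with the drug. Appendix 6 names tachycardia and bradycardia among the reasons to terminate a clamp. A summary restricted to completers of both clamps could thus omit some of the clamps that were tolerated worst.

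What is at stake is the completeness of a descriptive account of cardiovascular response under hypoglycemia.

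**Working it through.** **1. Planned numbers (Protocol 10.1, SAP 5.2).** The plan states 30 completers, 38 enrolled and 20% discontinuation. The inflation checks: 30 / 0.80 = 37.5, rounded up to 38. The 30 also checks. With a within-subject SD of 40 pg/mL, the expected half-width for n = 30 is t(0.975, 28) x 40 x sqrt(2/30) = 21.16 pg/mL. The probability that the half-width is within 23.65 is 0.83 at n = 30 and 0.79 at n = 29. No figure in the plan is in question.

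**2. How many clamps are affected.** Planned non-completers: 38 - 30 = 8. Let k be the number who finish the Period 1 clamp and then leave. The documents do not give k, so it runs from 0 to 8. Completers contribute 30 x 2 = 60 clamps, and the omitted share is k / (60 + k).

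- k = 0: 0%
- k = 2: 2/62 = 3.2%
- k = 4: 4/64 = 6.3%
- k = 8: 8/68 = 11.8%

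If retention is the same in each period (an assumption), it is sqrt(30/38) = 0.888 per period. About 38 x (1 - 0.888) = 4.2 patients then leave before the Period 1 clamp and 3.8 after it, so k is about 4. The value k = 8 would need every dropout to come after the Period 1 clamp and none during the first 12 weeks.

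**3. Effect on the treatment difference.** Each treatment has 30 completer clamps. Let kT and kP be the omitted tirzepatide and placebo clamps. Let dT and dP be the gaps between the leavers' and completers' mean pulse change on each treatment. Adding the omitted clamps moves the difference by

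kT/(30 + kT) x dT - kP/(30 + kP) x dP.

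The documents give no gap in bpm, so the values of d below are assumptions.

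- Even split, common gap (kT = kP = 4, dT = dP = 10): each mean moves 4/34 x 10 = 1.2 bpm and the difference moves 0.
- Even split, gap on tirzepatide only (dT = 10, dP = 0): 4/34 x 10 = 1.2 bpm.
- Two leavers, both after tirzepatide, d = 10: 2/32 x 10 = 0.6 bpm.
- All 8 after tirzepatide: 8/38 x d = 1.1, 2.1 or 4.2 bpm for d = 5, 10 or 20.

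**4. What still reaches the report for such a patient.** Treatment-emergent adverse events are summarised by treatment on the safety population (SAP 6.10.2). Adverse events leading to discontinuation are listed (6.10.4). Procedure-related adverse events are listed and, if frequent enough, summarised (Protocol 10.3.1.2). Safety listings cover all study periods (6.10). The listing of abnormal vital signs in 6.10.6 is not worded as limited to Days 1 to 78. However, it shows only values that cross the Table GPHG.8 thresholds, for example pulse above 100 with a rise of at least 15. None of these gives mean blood pressure or pulse at a plateau by treatment.

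**The case against.** The strongest reply is that the protocol already chose the PD home. A reader might infer that the SAP departs from a protocol promise to summarise clamp vital signs in all enrolled patients. The documents do not support that. Protocol 10.3.3.2 and the synopsis put this same summary among the PD measures, 10.3.1.2 itself refers to the PD section, and 10.3 sets completers of both clamps for PD. The safety label does not settle the population either: Protocol 9.4 also calls glucagon and the other hormones safety measures. The SAP names the section and the analysis set openly, so Section 8 had no clear change to record. This part of the reply stands in full.

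A reader might also infer that clamps stopped for safety are excluded. That is not shown. Clamps with a raised nadir are kept (Protocol 10.3.3.1, SAP 6.9.1), the Table GPHG.3 footnote accepts that plateau level and duration vary, and for plateau vital signs "If there is only one non-missing value, it will be used as the measurement". Neither document says what completing means for a terminated clamp, so neither inclusion nor exclusion can be claimed.

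Finally, for at most 8 patients, individual listings and adverse-event reports may tell a reader more than a small shift in a mean. This is fair, and it limits the weight of the point. It does not remove the gap, because readings below the abnormality thresholds need not appear in the one vital-sign listing that 6.10.6 specifies.

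**Conclusion.** The point holds as a minor, cheap improvement. The only by-treatment summaries of clamp blood pressure and pulse are in patients who complete both clamps. They leave out 0 to 8 Period 1 clamps of later leavers, about 4 under equal per-period dropout. The effect on the tirzepatide-placebo difference may be zero and is 2.1 bpm in the assumed one-sided extreme with a 10 bpm gap. The counts rest on the planned 38 and 30 and on all 30 completers entering the PD analysis set; the bpm values rest on assumed gaps.

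It would be tempting to read this as bias in the trial's main comparison. The documents do not support that reading: the primary endpoint is glucagon, and conditions during the clamp are monitored in real time whatever is tabulated later. Restricting the within-patient PD contrast to completers is defensible.

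**What to change.** In SAP 6.10.6, add one descriptive by-treatment table of clamp systolic blood pressure, diastolic blood pressure and pulse on the safety population. It should give plateau and recovery values and change from the 100 mg/dL plateau, use all available clamp readings, and show n at each plateau. Keep the Section 6.9 models and summaries on the PD analysis set. A by-treatment count of clamps terminated for safety is optional; the documents do not say whether termination is an eCRF field.

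The cost is SAP wording and one table. The readings are already collected, and no visits, samples or patients are added. The downside is that the table's N will differ from the PD table and that it mixes paired clamps with Period-1-only clamps, so a footnote should say it is descriptive and not a within-patient comparison.

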Study Period Day	-14 ±3 ^a or -42 ±3 ^a	-7 ±3 ^a or -35 ±3 ^a (prior to randomization)	1	1	Patients on metformin only should perform Visits 1 and 2 approximately 2 and 1 week prior to Visit 3. Patients on metformin and one additional OAM should perform Visit 1 about 6 weeks prior to Visit 3, in order to permit eligibility assessment at Visit 2. OAMs other than metformin will be discontinued immediately after Visit 2 followed by at least 4-weeks washout between Visit 2 and Visit 3.
Diagnostics					
PK sample			P	P	PK and immunogenicity to be time-matched as much as possible.
Immunogenicity			P	P	
Pharmacogenetic sample			P		Single sample taken predose on Day 1 Period 1.
Nonpharmacogenetic stored samples			P	P	Fasting sample.

Abbreviations: AE = adverse event; BP = blood pressure; ECG = electrocardiogram; FSH = follicle-stimulating hormone; P = predose; PK = pharmacokinetic; PR = pulse rate; SMPG = self-monitoring of blood glucose.

a Visit windows are relative to randomization (Period 1, Day 1).

b A serum pregnancy test will be taken during Visit 2 if the FSH ≤40mIU/mL at Visit 1.

Note: If multiple procedures take place at the same time point, the following order may be consulted for prioritization: ECG, vital signs, counter-regulatory hormone samples, safety laboratory tests, PK samples, immunogenicity samples, storage samples.

Study Schedule Protocol I8F-MC-GPHG: Treatment Periods 1 and 2

Procedure	Treatment Periods 1 and 2												Comments		
Visit Period 1	4	5		6			7			8	9	9			
Visit Period 2	11	12		13			14			15	16	16			
Study Period Week	2	3	4	5	6	7	8	9	10	11	12	12			
Study Period Day	8 ±1	15 ±1	22	29 ±1	36	43	50	57 ±1	64	71	78 ±2	79 ±2	80 ±2	Patients should attend on stated day. When the patient is unable to attend CRU on the stated day, visit windows should be used for dosing only. Days 78, 79, and 80 should occur consecutively, without interruption.	
Weight				P			P			P					
Vital signs (BP/PR/body temperature)	P	P		P			P			P	X See Appendix 6		Refer to screening table.		
ECGs				P						P	X See Appendix 6		Refer to screening table.		
Concomitant medications	X														
AEs	X														
Physical examination / medical assessments	X									X			Refer to screening table.		
Alcohol breath test											X				
CRU admission											X				
CRU discharge												X			
Outpatient visit	X	X		X			X			X					
Dispense study treatment		X		X			X						For outpatient use.		

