10.3.4. Evaluation of Immunogenicity

The frequency and percentage of patients with preexisting ADA and with TE-ADA+ to tirzepatide will be tabulated. Treatment-emergent ADA are defined as those with a titer 2-fold (1 dilution) greater than the minimum required dilution if no ADAs were detected at baseline (treatment-induced ADA) or those with a 4-fold (2 dilutions) increase in titer compared to baseline if ADAs were detected at baseline (treatment-boosted ADA). The minimum required dilution of the ADA assay is 1:10. For the TE-ADA+ patients, the distribution of maximum titers will be described. The frequency of neutralizing antibodies if performed, will be tabulated in TE-ADA+ patients. If cross-reactivity to native GLP-1 and GIP or neutralizing antibodies against native GLP-1 and GIP assays are performed, the frequency of each will be reported.

The relationship between the presence of antibodies and the tirzepatide concentrations and PD response including safety and efficacy to tirzepatide may be assessed.

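### Treatment-emergent anti-tirzepatide antibodies are not limited to samples, or to patients, after a first tirzepatide dose

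*SAP*

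**What the plan says.** SAP 6.11 fixes one baseline for both sequences and one table layout: "Baseline immunogenicity sample is collected on Day 1 pre-dose of period 1. The immunogenicity tables will be presented with only one overall column". It then adds: "The listings will report treatment and period".

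Protocol 10.3.4 gives the titer rule. A treatment-induced case has a "titer 2-fold (1 dilution) greater than the minimum required dilution if no ADAs were detected at baseline"; a treatment-boosted case has a "4-fold (2 dilutions) increase in titer compared to baseline if ADAs were detected at baseline". The minimum required dilution is 1:10. Neither limb mentions prior tirzepatide.

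SAP 6.11 names no analysis population. SAP 6.2 makes the safety population the default for safety analyses, and SAP Table GPHG.2 admits anyone given at least one dose of tirzepatide or placebo. Both objectives tables list the antibody frequency as an exploratory endpoint under other safety parameters. Protocol 10.3.4 commits to tabulating it; the SAP makes the table optional. SAP 6.11 also makes a TE-ADA-positive case an adverse event of special interest (AESI) when it is associated with a severe or serious hypersensitivity or injection-site reaction.

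The Schedule of Activities (Protocol 2) places predose immunogenicity samples at Visit 3, at Days 29 and 78 of each period, and at Visit 10, the first dose of Period 2. Protocol 9.6.4 adds samples at early termination and at safety follow-up.

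**The concern.** The reported quantity is meant to be the frequency of antibodies that emerge under tirzepatide. In a crossover, a patient's first dose of study drug and first dose of tirzepatide coincide in only one sequence. For placebo-first patients, everything from Visit 3 up to the Visit 10 predose sample is post-baseline under the SAP but precedes any tirzepatide.

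Two distortions become possible:

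- **Numerator:** a titer rise on placebo can be labelled treatment-emergent.
- **Denominator:** patients who never received tirzepatide can be counted as at risk.

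At stake are the tabulated percentage and the AESI flag that depends on TE-ADA status. No efficacy or primary pharmacodynamic result is involved.

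**Working it through.** **Does any other text close the gap?**

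- Protocol 9.5.1 says samples from placebo treatment are not planned for analysis, but that concerns the tirzepatide concentration assay, not antibodies.
- SAP 6.10.2 starts treatment emergence for adverse events at the first dose of Period 1, whichever treatment that is. Borrowing that convention would bring placebo-period samples in.
- SAP section 8 (changes from the protocol) does not mention antibodies.

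**Would a usual evaluability rule remove unexposed patients?** Not if it asks only for a baseline and one later result. Under Protocol 5.1.2 and 8.1.1, stopping treatment means leaving the study, so a placebo-first patient who stops before Period 2 never receives tirzepatide. That patient still gives an early-termination antibody sample.

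**Inputs.** The documents give no figure for the antibody analysis, only the trial size (Protocol 10.1, SAP 5.2): 30 completers, 20% discontinuation, 38 enrolled. This reproduces: 30 / (1 − 0.20) = 37.5, rounded up to 38. With 1:1 allocation (Protocol 5.1.1), 38 / 2 = 19 are placebo-first.

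**Patients never exposed, u.** The documents do not state u. If discontinuation is equal in both sequences, placebo-first losses over the whole study are 0.20 × 19 = 3.8. That total includes Period 2 losses, who have received tirzepatide. Splitting it evenly between periods gives 3.8 / 2 = 1.9. I take u = 2 as the central assumption and 0 to 4 as the range.

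**Denominator effect.** Printed rate = true rate × (38 − u) / 38, with an assumed true rate of 50% among exposed patients:

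| u | Exposed | True positives | Printed on 38 | On exposed |
|---|---|---|---|---|
| 0 | 38 | 19 | 50.0% | 50.0% |
| 2 | 36 | 18 | 47.4% | 50.0% |
| 4 | 34 | 17 | 44.7% | 50.0% |

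The arithmetic extreme, all 8 planned losses (38 − 30) being unexposed, gives 15/38 = 39.5%. It would require every dropout to be placebo-first and to leave before Period 2.

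**Numerator effect.** Let f be the assumed chance that a placebo-first patient meets the titer rule on any pre-tirzepatide sample. The expected number is 19f, and the chance of at least one is 1 − (1 − f)^19:

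| f | Expected number | Chance of at least one |
|---|---|---|
| 1% | 0.19 | 17% |
| 2% | 0.38 | 32% |
| 5% | 0.95 | 62% |

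Each such patient who would not have turned positive later on tirzepatide adds 1/38 = 2.6 points.

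**Together.** The effects oppose each other. With u = 2 and one added false positive, the table shows (18 + 1) / 38 = 50.0%, which looks right by accident. With u = 0 and one false positive it shows 20/38 = 52.6%.

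**The case against.** The strongest reply is that this is silence, not error. SAP 6.11 never says that placebo-period samples qualify, and it describes the tabulated result as antibodies to tirzepatide. Its parts differ in weight:

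- **The baseline is valid.** Prior tirzepatide exposure is excluded (Protocol 6.2, criterion 34), so Visit 3 is drug-naive for everyone and suits preexisting antibodies. This stands. A reader might infer that the Period 1 baseline is wrong for placebo-first patients; the documents do not support that. What is missing is a rule on which later samples and patients count.
- **The denominator is inferred.** Section 6.11 lies outside the SAP's safety analyses section, and the protocol puts immunogenicity assessments under pharmacodynamics. This stands in part. The safety population is the default reading, because the endpoint is listed as a safety parameter and no other set is named, but it is not stated.
- **Titer rules are demanding.** Ordinary assay variation does not automatically give a rise of one dilution above the minimum, still less a 4-fold rise. This stands, and no false-positive rate can be taken from the documents.
- **The listings show treatment and period.** In a trial of about 38, affected cases can be traced by hand. This stands as mitigation, but it leaves the percentage and the AESI flag uncorrected.
- **The single column is reasonable.** Antibodies raised in Period 1 may persist, so by-treatment columns could credit them to placebo. This stands. A reader might infer that pooling is itself the fault; it is not.

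**Conclusion.** The point holds as a gap in definition. Followed literally, the two documents allow a placebo-first patient to be TE-ADA-positive before any tirzepatide, and allow never-exposed patients into the denominator. They do not show that either will happen, nor that the SAP intends it.

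Under the assumptions above, the denominator effect takes a true 50% to between 50% and 45%, and to about 47% in the central case. Pre-exposure positives offset or reverse this by up to 2.6 points each. The true rate, the number unexposed, the false-positive rate and the safety-population denominator are all assumptions.

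It would be tempting to treat the 3.8 placebo-first losses as patients lost before tirzepatide. The 20% covers the whole study, so 3.8 is an upper figure if discontinuation is equal in both sequences.

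Severity is low: an exploratory, descriptive endpoint, with no effect on the primary analysis. It is worth correcting because the correction is nearly free and the TE-ADA flag feeds an AESI category.

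**What to change.** Add three sentences to SAP 6.11:

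1. TE-ADA is assessed only on samples after the first tirzepatide dose, relative to the last sample before that dose: normally Visit 3 if tirzepatide-first and Visit 10 predose if placebo-first.
2. The denominator is patients with at least one tirzepatide dose, a baseline result and at least one later antibody result.
3. The Period 1 Day 1 sample remains the reference for preexisting antibodies, and the single overall column is kept.

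The baseline rule is needed as well as the sample rule. Otherwise a rise that occurred on placebo and persisted would still be credited to tirzepatide. Antibody results from placebo-first patients before tirzepatide stay in the listings. The AESI rule should use the same TE-ADA definition.

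The cost is SAP wording, an entry in SAP section 8, and minor programming. Every sample is already scheduled. Protocol 10.3.4 leaves the baseline sample unspecified, so the clarification does not appear to change a principal feature, which is the SAP 6.2 test for needing a protocol amendment.
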